6.3.2 Adverse events

Adverse events will be assessed throughout the duration of the study. All adverse events will be categorized with respect to severity and device-relatedness.

The following skin reactions are an expected outcome related to treatment:

- Dryness
- Sloughing/flaking of skin
- Infection
- Presence of prolonged erythema
- Presence of prolonged edema
- Burn / Blistering
- Hyperpigmentation
- Hypopigmentation
- Contact dermatitis
- Pruritus/Scarring
- Herpes simplex virus outbreak

Reports of all adverse events by subjects and investigator will be documented in the source documents and will be recorded in the Adverse Events form.

6.4 Subject Discomfort Evaluation

Subject assessment of discomfort and pain from the procedure will be evaluated using a 100 mm Visual Analogue Scale (VAS), where 0 mm is "no pain" and 100 mm is "intolerable pain".

Immediately after treatment the subject will be asked to rate treatment related pain. The subject will be presented the CRF page with the VAS (below) with words along a horizontal line and asked to make a mark along the 100 mm scale, representing their pain from no pain to intolerable pain (must stop the treatment). A

number will be derived by the research staff by measuring up to the point the subject has indicated versus the entire line.

Figure 2: Visual Analogue Scale (VAS)

No pain

Pain as bad as it can be

The CRF page with the VAS will be considered to be a source document.

7 Study Analysis Plan

7.1 Statistical and Analytical Plans

This is the basis for the Statistical Analysis Plan for this study. This plan may be revised during the study to accommodate amendment to this Protocol and to make changes in relation to unexpected issues in study execution and data that affect planned analyses. Revisions to this protocol will be based on independent review of the study data and a final plan will be issued prior to data lock.

7.2 Study Hypothesis

The study hypothesis is that the treatment using Diamondpolar applicator followed by AC DUAL applicator and the AC DUAL applicator will improve the appearance of Acne Vulgaris by at least 2 points on the Global Acne Assessment Score (GAAS), at 6 weeks follow-up compare to baseline in the study population.

7.3 Sample Size Justification

This pilot study will enroll up to 50 patients in order to evaluate the safety and the efficacy of the treatment of acne using the Diamondpolar applicator followed by AC DUAL applicator and the AC DUAL applicator alone.

7.4 Study Analysis

- All subjects will be evaluated for efficacy and safety data at baseline, during treatments and at 6-week post treatment visit.
- The analysis set will be as complete as possible and as close as possible to ensure it complies with the intent-to-treat principle for all enrolled subjects
- Subject demographics, baseline assessments, treatment parameters, treatment evaluations, follow-up assessments and reported adverse events will be summarized and analyzed using the following statistical tools:
 - All summary tables for quantitative parameters will display mean, standard deviation, median and applicable descriptive statistics. Correlations between variables will also be performed where applicable.
 - All summary tables for qualitative parameters will show counts, percentages and orders.
 - Number of missing data will be displayed on all tables where applicable.
 - Inter-rater reliability test will be performed to assess agreement between reviewers.
 - All statistical tests will be two-sided. The level of statistical significance for effectiveness analyses is 5% ($\alpha = 0.05$) for all tests of differences. Paired t-test and/or Wilcoxon Signed-

Ranks Test for Matched Pairs will be used to compare the evaluations at the baseline and post treatment sessions.

- For all primary and secondary end-point data generated in this study, applicable data analysis tools listed above will be used to determine if the study meets its efficacy and safety criteria.

8 Adverse Events

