
Objectives
	
Primary objectives
 
 • To evaluate the efficacy of facial acne vulgaris treatment using the Venus Versa (MP)² Diamondpolar applicator in combination with the Venus Versa AC dual applicator using two Intense Pulsed Light Wavelength Bands • To evaluate the efficacy of facial acne vulgaris treatment of the Venus Versa AC dual applicator using two Intense Pulsed Light Wavelength Bands. 
Secondary objectives
 
 • To evaluate subject's assessment of improvement & satisfaction. • To evaluate subject's assessment of comfort with the treatments. • To compare the efficacy of the combination treatment and IPL treatment alone.

Hypothesis
	
Both the combination treatment and the IPL treatment will result in Acne Vulgaris improvement. Improvement will be defined as achieving improvement of at least 2 points on the 5-point Global Acne Assessment Score (GASS) at FU (6 weeks following the last treatment) as compared to baseline.

Criteria for Evaluation
	
Efficacy
 
Primary endpoint:
 
 • Acne Vulgaris improvement by at least 2 points on the Global Acne Assessment Score (GASS) from photographs 6 weeks following the last treatment - FU, as compared to baseline, based on before/after photos, as determined by up to 3 independent reviewers (dermatologists and/or plastic surgeons). 
Secondary endpoints: Subject Evaluation, Comfort & Satisfaction
 
 • Reduction of inflammatory lesions and non-inflammatory lesions as determined by investigator based on lesion count. • Improvement in subject satisfaction assessment scale with treatment outcome based on a 5-point Likert scale. • Improvement in subject self-assessment of Acne Vulgaris according to the Global Aesthetic Improvement Scale (GAIS) from photographs 6 weeks following the last

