procedure. At the first treatment visit, the investigator will collect demographic and medical information and perform 3 test spots to evaluate skin sensitivity and choose appropriate presets. Subjects with skin type IV-V will be monitored 48-96 hours after the test spot for their skin reaction. Subjects that demonstrate excessive skin reaction to the test spot will be withdrawn from the study and will not be included in the study efficacy population or in the safety analysis since study treatment has not occurred. Should a subject (or the subject's legally authorized representative) decide to voluntarily withdraw, all efforts will be made to collect and report the final visit observations, and the reasons for withdrawal, as thoroughly and timely as possible. Withdrawals will be documented in the CRF and reported to local institutional review board (IRB) or ethical committees as required. The first treatment visit may occur on the same day as the screening visit but can be scheduled up to 30 days after the screening.

The duration of the treatment session will be approximately 40 minutes depending on the treated area size. Expected immediate response includes temporary mild to moderate erythema and/or edema. Skin safety assessments will be conducted by the investigator after each treatment session and at follow-up visits. Photography will be conducted at baseline, the beginning of last visit and at FU. The level of the subject's discomfort will be documented at the end of each treatment session. Subject satisfaction will be evaluated at FU. Evaluation by up to 3 independent reviewers will be based on before/after pictures of the baseline, before the last treatment and at the 6 week follow up visit using GAAS.

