3.2 Secondary effectiveness endpoints

- Reduction of inflammatory lesions and non-inflammatory lesions.
- Subject Improvement assessment in treated area appearance at 6 weeks after the last treatment compared to baseline using the Global Aesthetic Improvement Scale (GAIS).
- Subject assessment of pain and discomfort associated with treatments using a 100 mm Visual Analogue Scale (VAS), were 0 is "no pain" and 10 is "intolerable pain".
- Subject's satisfaction with treatment outcome based on a 5-point Likert scale.
- Subject improvement assessment of "quality of life" using QOL Questionnaire.
- Comparison of the two treatments for the primary and secondary endpoints.

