3.5 Schedule of Times and Events

The following table provides a summary of the required study visits and the procedures and assessments to be performed at each visit. Details of the procedures and assessments will be described subsequently in the protocol.

Table 1: Study Procedures - CS2715

Tx=Treatment; FU=Follow Up

Visit#	Visit #1	Visit #2	Visit #3	Visit #4	Visit #5	Visit #6
Study Activities	Screening & Test spot	Tx1	Tx2	Tx3	Tx4	FU
Timing (see Figure 1)		0-7 days post given ICF	1 week + 5 days post 1 st TX	2 weeks + 5 days post 1 st TX	3 weeks + 5 days post 1 st TX	6 weeks + 7 days after last Tx
Informed Consent	X					
Eligibility assessment	X					
Demographic information	X					
Medical/surgical history	X					
Physical examination	X					
Urine pregnancy test	X					X
Test spots	X					
Photographs		X			X	X
Lesion Count (FACE)	X	X	X	X	X	X
Treatment		X	X	X	X	
Immediate/short term response		X	X	X	X	
Subjects discomfort assessment (VAS)		X	X	X	X	
Subject improvement evaluation using GAIS						X
Subject satisfaction assessment scale (5-point Likert scale)						X
Subject improvement assessment of "quality of life" using QOL Questionnaire	X		X	X	X	X
Independent reviewer improvement evaluation using GAAS						X
Adverse events		X	X	X	X	X
Concomitant medications		X	X	X	X	X

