3.6 Concurrent Control

For the primary endpoints, there is no concurrent control in this study. Each patient's efficacy results will be compared to baseline. A comparison between treatment will be performed as a secondary endpoint.

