5.2 Treatment visits

Each subject will be enrolled, randomly assigned to AC DUAL treatment (IPL alone) or Diamondpolar treatment (RF + PEMF) followed by AC Dual treatment (IPL) and scheduled for 4 treatments at 1 week intervals (\pm 5 days) and return for follow-up visit at 6 weeks after the last treatment (\pm 7 days) for evaluation of the treated areas. The duration of the entire treatment visit is approximately 40 minutes. During each visit various tasks will be performed.

The following procedures and assessments are required at the treatment visits:

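### Combination versus IPL alone is a stated secondary comparison of randomised arms, but the only tests of difference named are within-subject tests; no between-arm estimate, test or interval is given.

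*Combined protocol and SAP*

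**What the plan says.** The comparison is promised in several places. The synopsis lists as a secondary objective "To compare the efficacy of the combination treatment and IPL treatment alone". Section 3.2 lists as a secondary endpoint "Comparison of the two treatments for the primary and secondary endpoints". Section 3.6 states that "A comparison between treatment will be performed as a secondary endpoint", and the opening of section 6 repeats the efficacy comparison among the secondary endpoints.

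The arms are independent groups: under section 5.2 each subject is "randomly assigned to AC DUAL treatment (IPL alone) or Diamondpolar treatment (RF + PEMF) followed by AC Dual treatment (IPL").

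Section 7.4 lists means, SDs and medians; counts and percentages; missing-data counts; correlations; inter-rater reliability; and the paired t-test and/or Wilcoxon signed-ranks test, where the "Ranks Test for Matched Pairs will be used to compare the evaluations at the baseline and post treatment sessions". It then says that for all primary and secondary endpoint data the "applicable data analysis tools listed above will be used to determine if the study meets its efficacy and safety criteria". The only other named test, in section 3.1, is again the signed-ranks test for matched pairs.

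Section 7.1 calls section 7 the basis for the SAP and commits to a final plan before data lock. Section 7.3 describes a pilot of up to 50 patients.

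**The concern.** A paired test takes two measurements on the same person. Combination and IPL alone are given to different people, so neither named test can address the difference between them. An analyst who follows this version reaches the secondary objective with summary tables by arm and no prescribed way to estimate the difference or state its uncertainty.

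This is the study's only randomised contrast, and so its only controlled information on what the Diamondpolar step adds to IPL. The before-after results in each arm cannot separate a treatment effect from natural fluctuation or regression to the mean; the between-arm difference is protected from those for the added component. With few subjects per arm, an unqualified gap between two columns of a table is easily over-read.

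**Working it through.** **1. What is asked and what is supplied**

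| Requirement | Where | Method named |
|---|---|---|
| Change from baseline, GAAS | 3.1, 7.4 | Signed-ranks; paired t-test and/or signed-ranks |
| Change from baseline, other evaluations | 7.4 | Paired t-test and/or signed-ranks |
| Agreement between reviewers | 7.4 | Inter-rater reliability |
| Combination versus IPL alone, all endpoints | Synopsis, 3.2, 3.6, 6 | None |

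The two-sided 5% level in 7.4 fixes an error rate for tests of differences but names no between-group test. No confidence interval is named for the arms.

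**2. What data each endpoint offers**

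This decides which two-sample method fits.

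- Lesion counts: Table 1 schedules them at screening, before treatment and at follow-up, so a baseline is available for adjustment.
- QOL: collected at screening and at follow-up, so a baseline is available.
- Satisfaction, GAIS and VAS: no baseline. Section 3 says "The level of the subject's discomfort will be documented at the end of each treatment session. Subject satisfaction will be evaluated at FU", and Table 1 places the row "Subject improvement evaluation using GAIS" at follow-up only. The arms can be compared only on the post-treatment value.
- GAAS: section 3.1 uses baseline scores, Table 1 schedules GAAS at follow-up only, and section 6.1.1 has reviewers grade improvement from photograph pairs. Until these are reconciled, the arms can be compared on the change or improvement grade, but a baseline adjustment cannot be specified.

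**3. How wide the interval would be**

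The plan gives no SD, effect size or power for this comparison, so there is no figure to reproduce. Inputs:

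- *n* = 10 per arm: the 20 completers under the amendment 2 parameters (synopsis), assumed split 1:1.
- *n* = 25 per arm: the maximum of 50, assumed split 1:1. This is a best case, with no dropout and subjects treated under different parameters pooled.
- SD of GAAS change: 0.7, 1.0 or 1.3 points (assumed).

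Half-width = t(0.975, 2n−2) × SD × √(2/n).

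- *n* = 10: 2.101 × 0.447 = 0.940 per unit SD.
- *n* = 25: 2.011 × 0.283 = 0.569 per unit SD.

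| SD | n = 10 per arm | n = 25 per arm |
|---|---|---|
| 0.7 | ±0.66 | ±0.40 |
| 1.0 | ±0.94 | ±0.57 |
| 1.3 | ±1.22 | ±0.74 |

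Suppose the arms differ by 0.5 points in mean change with SD 1.0. At 10 per arm the interval is 0.5 ± 0.94, or −0.44 to 1.44. At 25 per arm it is 0.5 ± 0.57, or −0.07 to 1.07. Only at 25 per arm with SD 0.7 would a 0.5-point gap exclude zero (0.10 to 0.90).

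**4. If the 2-point criterion is read as a responder rate**

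Take 8/10 against 5/10. Wilson limits are 0.490 to 0.943 and 0.237 to 0.763. Newcombe limits for the difference of 0.30:

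- lower: 0.30 − √[(0.800 − 0.490)² + (0.763 − 0.500)²] = −0.11
- upper: 0.30 + √[(0.943 − 0.800)² + (0.500 − 0.237)²] = 0.60

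A 30-percentage-point gap is then compatible with anything from −11 to +60 points (Fisher p = 0.35).

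**5. Which interval suits whole-point grades**

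Simulated whole-point changes were bounded at −1 or −2 below and 3 above, with SD 1 before rounding, 10 per arm and 4,000 runs per scenario. The Welch interval covered the true difference in about 95% of runs. The Hodges-Lehmann interval moves only in whole points and was exactly 2 points wide in about 70% of runs. This favours the difference in means with a Welch interval as the lead result and the rank-sum test as support.

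**The case against.** The strongest reply is that section 7 is expressly provisional. Section 7.1 commits to a final plan before data lock, which is early enough to fix a secondary, exploratory method. That stands as to timing: the method is deferred, and the gap can still be closed properly. It does not close it, because 7.1 says nothing about what the method will be.

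A reader might infer that 7.4 rules out any between-arm test. The documents do not go that far. The sentence on the listed tools concerns whether the study meets its efficacy and safety criteria, and the stated efficacy criteria are before-after ones: a 2-point GAAS gain (3.1, 7.2) and a 25–50% lesion reduction (1.2). The section never says that only these tools may be used. The supportable statement is that no suitable method is named.

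A reader might also infer that the uncertainty would stay hidden. If the planned means, SDs and counts are tabulated by arm, an interval can be worked out from them. That is weaker than a planned interval but not nothing.

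Nor does the plan say that the arms will be compared by setting one within-arm p-value beside the other. That would be a misuse, and the documents do not prescribe it.

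Finally, the widths above mostly reflect the small sample, and naming a method will not narrow them. That is true, and it is a reason to report the interval.

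**Conclusion.** The point holds as an omission that should be fixed. A stated secondary objective in independent randomised arms has no named between-arm estimate, test or interval, and the tests of difference that are named cannot serve it. The final plan promised in 7.1 is the place to supply one.

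The size rests on assumptions outside the documents: 1:1 allocation and an SD of GAAS change of 0.7 to 1.3 points. Under these the 95% half-width is 0.66 to 1.22 points at 10 per arm and 0.40 to 0.74 at 25 per arm. That is wide enough, against a 2-point success criterion, for a by-arm table alone to mislead.

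The comparison is exploratory in a pilot. The gap does not itself affect the before-after primary analysis, but that is not an endorsement of it: the GAAS scoring descriptions in 3.1, Table 1 and 6.1.1 need separate reconciling.

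**What to change.** Add to section 7.4, or to the final plan before data lock:

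> For each endpoint in section 3.2, the exploratory result is the between-arm difference (combination minus IPL alone) with its 95% confidence interval.
>
> - Inflammatory and non-inflammatory lesion counts at 6 weeks (separately), and QOL at follow-up: ANCOVA on arm and baseline value.
> - GAAS change or improvement grade, GAIS, satisfaction, and each subject's mean VAS over Tx1–Tx4: difference in means with Welch interval as the lead result; rank-sum test as support.
> - If GAAS is analysed as a 2-point responder rate: difference in proportions with Newcombe interval.
>
> Within-arm p-values will not be used to compare arms.

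State also, before data lock:

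- which baseline is used (for example, the pre-Tx1 lesion count and the screening QOL score);
- how the scores of up to three reviewers are combined into one GAAS value per subject;
- which subjects are compared: those treated under the amendment 2 parameters, or all randomised.

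Another two-sample method for lesion counts or QOL would also serve, provided it is fixed in advance.

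The cost is a paragraph in a document already promised. Every assessment used is already in Table 1, so there are no new visits, patients or measurements. The downside is that wide intervals will be on open display.

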8.1 Adverse Events Definitions

In this study, an Adverse Event (AE) is any undesirable clinical occurrence (sign, symptom, illness, or other medical event), that appears or worsens during the clinical study, or requires medical treatment or intervention to a subject, whether it is considered to be device related or not. If an adverse event occurs, the first concern will be the safety and welfare of the subject. Appropriate medical intervention will be made.

Any AE or complication reported by the subject or observed by the physician that occurs during or after treatment with the device will be recorded in the subject's medical record or source document and on the Adverse Event Case Report Form. The investigator will determine if the AEs are device related or procedure related. This assessment shall include the onset date, resolution date, severity, seriousness, frequency, treatment and outcome.

Each AE should be assessed according to the following criteria:

8.1.1 Severity

Each AE should be assessed for its severity, or the intensity of an event experienced by the subject.

Mild: Awareness of a sign or symptom that does not interfere with the subject's activity or is transient resolved without treatment and has no sequelae.

Moderate: May interfere with the subject's usual activity and require additional intervention and/or treatment, and may have additional sequelae.

Severe: Significant discomfort to the subject and/or interferes with the subject's activity. Additional intervention and or treatment are necessary. Additional sequelae occur. Severe is used to describe the intensity of an event experienced by the subject.

8.1.2 Relationship of AE to the Device

Each AE should be assessed for its relationship to the device or procedure as identified as follows:

Device: This category should be restricted to adverse events directly attributable to the effect of the device.

Procedure: A procedure is any activity that supports the usage of the device.

Use the following categories for assigning the certainty of the relatedness:

Related: The AE is known to occur with the study agent, there is a reasonable possibility that the study agent caused the AE, or there is a temporal relationship between the study agent and event. Reasonable possibility means that there is evidence to suggest a causal relationship between the study agent and the AE.

Not Related: There is not a reasonable possibility that the administration of the study agent caused the event, there is no temporal relationship between the study agent and event onset, or an alternate etiology has been established.

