3.3 Safety

- Safety will be evaluated based on the number and type of any adverse event recorded throughout the study. Adverse events will be reported and categorized based on severity and device-relatedness. In addition, immediate response following treatment associated with various settings (e.g., erythema, edema, purpura, etc.), although expected results of treatment that are not considered adverse events, will be collected and reported for purposes of completeness. Information will also be captured on the intensity of response and the time required for resolution.

3.4 Study duration:

Duration of subject's participation: Up to 11 weeks from enrollment to termination (see Figure 1).

Study duration for entire study sample: Estimated to be 16 months from enrollment of first subject to the termination of the last. This is based on estimate of 8 months for recruitment + 2 months subject participation + 1 months collecting data.

Figure 1: Subject Participation

Time Intervals		1 week	1 week	1 week	1 week	6 weeks
	Enrollment	Treatment 1	Treatment 2	Treatment 3	Treatment 4	Follow-up
Timeline	Screening	Week 1	Week 2	Week 3	Week 4	Week 10

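### Section 8.1.2 lets an adverse event that follows treatment be both Related and Not Related, so the device-relatedness breakdown is not reproducible across investigators

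*Combined protocol and SAP*

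**What the plan says.** Section 3.3 states that "Adverse events will be reported and categorized based on severity and device-relatedness"; the synopsis and 6.3.2 say the same in substance. Section 8.1 leaves the decision on relatedness to the investigator.

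Section 8.1.2 offers two certainty labels. An event is Related if it is a recognised effect of the study agent, or if "there is a reasonable possibility that the study agent caused the AE, or there is a temporal relationship between the study agent and event". The definition of Not Related begins "There is not a reasonable possibility that the administration of the study agent caused the event" and continues with two further alternatives: "there is no temporal relationship between the study agent and event onset, or an alternate etiology has been established". There is no third label, no order of precedence, and no statement of how close in time an event must be to count as temporally related. The same section confines the Device category to events that can be attributed straight to the device's effect.

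In 8.1.1, a Moderate event may interfere with the subject's "usual activity and require additional intervention and/or treatment, and may have additional sequelae". A Severe event causes significant discomfort, or interferes with activity, or both, and the text adds: "Additional intervention and or treatment are necessary. Additional sequelae occur".

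**The concern.** Two labels that are meant to be opposites should not both fit the same event. Here they can, because a single condition from either list is enough and the lists are not complements of each other. An investigator who applies the timing condition and one who applies the alternate-cause condition can label the same event oppositely, and both will have followed the protocol.

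The consequence falls on one of the two axes along which the plan categorizes adverse events. The study is multi-center and open label. The masking in 3.7 covers only the readers of the photographs, so the person choosing the label knows the treatment. I found no adjudication step that would bring discordant labels into line.

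**Working it through.** The plan gives no figure on this point, so the check is one of logic.

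**Inputs, all from 8.1.2.** A = known to occur with the study agent; B = reasonable possibility of causation; C = temporal relationship; D = alternate etiology established.

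- Related = A or B or C
- Not Related = (not B) or (not C) or D

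**Literal reading.** Four yes/no conditions give 2 × 2 × 2 × 2 = 16 combinations.

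- Related only requires B and C and not D, with A free: 2 combinations.
- Not Related only requires not A, not B and not C, with D free: 2 combinations.
- Neither: 0.
- Both: 16 − 2 − 2 = 12.

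**Where C holds (8 combinations).** Every one is Related through timing. Not Related then reduces to (not B) or D, which fails only for B with not D, so 2 are Related only and 6 meet both. None is Not Related only. As written, an event that follows treatment can never be cleanly Not Related.

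**Does a kinder reading remove the overlap?**

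| Reading of Not Related | Meet both | Related only | Not Related only | Neither |
|---|---|---|---|---|
| As written | 12 | 2 | 2 | 0 |
| (not B and not C) or D | 8 | 6 | 2 | 0 |
| not B and not C and D | 1 | 13 | 1 | 1 |

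The overlap nearly disappears only when every or in the definition is replaced by and, which is not what the text says.

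**Cases the protocol itself can produce.** Contact dermatitis is on the list of expected skin reactions in 6.3.2, and subjects are supplied with sunscreen (5.2.3.3). Dermatitis a few days after treatment that is traced to the sunscreen satisfies A and C, so it is Related; it also satisfies D, so it is Not Related. With treatments about a week apart (5.2), a cold between visits satisfies C if a few days counts as temporal, and also fails B.

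**The Device sentence.** An event that is Related through timing alone is not one that can be attributed straight to the device. The two parts of 8.1.2 therefore pull in opposite directions, and nothing says which governs a count of device-related events.

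**Severity (8.1.1).** Let I = interference, S = significant discomfort, T = treatment needed, Q = sequelae. Severe = (S or I) and T and Q, which holds in 3 combinations. If Moderate needs only T, because the rest is worded permissively, all 3 are also Moderate. If Moderate needs I and T, 2 of the 3 are.

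**The case against.** The strongest reply is that safety in 3.3 rests first on the number and type of adverse events, and that immediate skin responses, their intensity and their time to resolution are reported separately. Section 8.1 also records onset, resolution, seriousness, frequency, treatment and outcome. None of these depends on 8.1.2. Under 8.2.1, serious events go to the monitor whether or not they are thought device-related. All of this stands. A reader might infer that the whole adverse event table is arbitrary, and the documents do not support that.

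A second reply is that the Device sentence already limits what may be called device-related. It does constrain the count, but it contradicts the timing condition and the text does not say that it overrides it.

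Third, a reader might infer that any event with some other plausible cause is also Not Related through the alternate-etiology condition. The text requires that cause to be established, which is a higher bar. A reader might also infer damage to a safety comparison of combination treatment against IPL alone. Section 3.2 plans the treatment comparison for the primary and secondary endpoints, safety sits under its own heading, and the stated objective is to compare efficacy.

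Finally, Moderate and Severe are adjacent grades, and assigning the highest grade fully met is an ordinary way to read an ordered scale. That is fair. The severity overlap needs a tie-break, and rebuilding the scale would be a matter of preference.

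**Conclusion.** The point holds for the relatedness breakdown. As written, 12 of 16 logical combinations meet both definitions, 6 of 8 do so where the event follows treatment, and the stated rules give no way to choose. The breakdown is therefore not reproducible across unblinded investigators and sites. Some events remain unambiguous: a reasonable possibility with compatible timing and no other established cause is Related only.

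The severity overlap is real but lesser. The number and type of events, the grading of immediate responses and the first report of serious events to the monitor are unaffected.

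This rests on reading or in its ordinary sense and on there being no precedence or adjudication rule in the documents. The combinations are logical cases and carry no weights. The documents give no adverse event rates, so the share of real events affected, and any range for the device-related percentage, cannot be computed.

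**What to change.** Rewrite the two labels in 8.1.2 around one judgement:

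- **Related:** there is a reasonable possibility that the device or procedure caused or contributed to the event. Compatible timing is necessary but not sufficient.
- **Not Related:** there is no such possibility, because the timing is incompatible or an established alternate etiology fully explains the event.
- **Unclear cases**, including those where neither reason for Not Related can be shown, default to Related.

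Timing and other causes then become evidence for a single yes/no decision, so no event can carry both labels or neither. Align the Device and Procedure wording with this. In 8.1.1, add that an event meeting both Moderate and Severe takes the higher grade.

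The cost is a short amendment under 9.7, matching instructions on the adverse event form, and one re-read of events already recorded, before the safety tables are produced. The related count may move either way: removing timing alone as a sufficient condition narrows the category, and the default for unclear cases widens it.
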